## 9.2.3 Additional Adverse Event Severity Grading

Pulse and BP# will be graded as follows:

Table 9: Pulse and BP Adverse Event Grading

Physiologic Parameter	Mild (Grade 1)	Moderate (Grade 2)	Severe (Grade 3)
Bradycardia – beats per minute	45 – 50	40 – 44	<40

\* A fever can be considered not related to the study product if an alternative etiology can be documented.

† Participants must not eat or drink anything hot or cold, or smoke within 10 minutes prior to taking oral temperature.

Tachycardia – beats per minute	101 – 130	131 – 155	>155
Hypotension (systolic) mmHg	80 – 84	75 – 79	<75
Hypotension (diastolic) mmHg	50 – 54	45 – 49	<45
Hypertension (systolic) mmHg	141 – 155	156 – 160	>160
Hypertension (diastolic) mmHg	91 – 100	101 – 110	>110

<sup># Pulse and BP assessed on Day 1 prior to the first study vaccination will be considered as baseline.

Clinical safety laboratory values will be graded as follows:

**Table 10: Clinical Safety Laboratory Adverse Event Grading** 

Panel and Analyte a	Mild (Grade 1)	Moderate (Grade 2)	Severe (Grade 3)	
Serum Chemistry				
Blood Urea Nitrogen (mg/dL)	23–26	27–31	>31	
Creatinine (mg/dL) female	1.3–1.7	1.8–2.0	>2.0	
Creatinine (mg/dL) male	1.4–1.7	1.8–2.0	>2.0	
Alkaline phosphatase (U/L) female	147-196	197-294	>294	
Alkaline phosphatase (U/L) male	192-256	257-384	>384	
ALT(U/L)	68-113	114-225	>225	
Total Bilirubin when accompanied by any grade ALT (mg/dL)	1.3-1.6	1.7-2.0	>2.0	
Total Bilirubin when not accompanied by any grade ALT (mg/dL)	1.3-2.0	2.1-2.6	>2.6	
Hematology				
Hemoglobin, female (g/dL)	10.0-10.9	9.0-9.9	<9.0	
Hemoglobin decrease from baseline value, female (g/dL)	1.0–1.5	1.6–2.0	>2.0	
Hemoglobin, male (g/dL)	11.5-12.4	10.5-11.4	<10.5	
Hemoglobin decrease from baseline value, male (g/dL)	1.0–1.5	1.6–2.0	>2. 0	
WBC (leukocytosis) (cell/mm³)	12,001–15,000	15,001–20,000	>20,000	
WBC (leukopenia) (cell/mm  )	2,500–2999	1,500–2,499	<1,500	

Panel and Analyte a	Mild (Grade 1)	Moderate (Grade 2)	Severe (Grade 3)
Eosinophils (absolute eosinophilia) (cell/mm³)	1201-1500	1,501–5,000	>5,000
Neutrophil (neutropenia) (cell/mm³)	1001-1200	751-1,000	<751
Platelets (thrombocytopenia)(cell/mm³)	100,000– 126,000	50,000-99,999	<50,000

ALT = alanine aminotransferase; WBC = white blood cell.

#### 9.2.4 Serious Adverse Events

**Serious Adverse Event (SAE)**: An AE or suspected adverse reaction is considered "serious" if, in the view of either the site PI (or appropriate sub-investigator) or sponsor, it results in any of the following outcomes:

- Death,
- A life-threatening AE\*,
- Inpatient hospitalization or prolongation of existing hospitalization,
- A persistent or significant incapacity or substantial disruption of the ability to conduct normal life functions, or
- A congenital anomaly/birth defect.
- Important medical events that may not result in death, be life-threatening, or require hospitalizations may be considered serious when, based upon appropriate medical judgment they may jeopardize the patient or participant and may require medical or surgical intervention to prevent one of the outcomes listed in this definition. Examples of such medical events include allergic bronchospasm requiring intensive treatment in an emergency room or at home, blood dyscrasias or convulsions that do not result in inpatient hospitalization, or the development of drug dependency or drug abuse.

<sup>a Laboratory normal reference ranges have been taken into consideration for the toxicity grading scale. If the laboratory provides a value that has additional significant digits beyond what is provided in the table, digits of 0-4 will be rounded down and digits of 5-9 will be rounded up, for purposes of delineating a grade.

\* Life-threatening AE: An AE is considered "life-threatening" if, in the view of either the site PI (or appropriate sub-investigator) or sponsor, its occurrence places the patient or participant at immediate risk of death. It does not include an AE that, had it occurred in a more severe form, might have caused death.

#### SAEs will be:

- Assessed for severity and relationship to study product or alternate etiology (if not related to study product) by a licensed study physician listed on the Form FDA 1572 as the site PI or sub-investigator.
- Recorded on the appropriate SAE form and entered into the eCRF.
- Followed through resolution by a licensed study physician listed on the Form FDA 1572 as the site PI or sub-investigator.
- Reviewed and evaluated by the SMC (periodic review unless related), DMID, and IRB, as required.

## 9.2.5 Procedures to be Followed in the Event of Abnormal Laboratory Test Values or Abnormal Clinical Findings

The site PI or appropriate sub-investigator is responsible for recording all AE/SAEs that are observed or reported during this trial, regardless of relationship to study product. AE/SAEs, abnormal laboratory test values, or abnormal clinical findings will be collected, assessed, documented, reported, and followed appropriately, using a local laboratory as necessary. In determining eligibility, refer to Section 5.1 and the protocol-specific MOP.

## 9.3 Reporting Procedures

Solicited injection site and systemic reactogenicity events will be documented and reported from the time of each study vaccination through 7 days after each study vaccination. These recording intervals are Days 1 through 8, inclusive, and Days 15 through 22, inclusive. If reactogenicity events are still present on Days 8 or 22, they will continue to be recorded until resolved.

Clinical safety laboratory AEs will be documented and reported following the post-vaccination clinical safety laboratory studies collected on approximately Day 29.

Unsolicited non-serious AEs will be documented and reported from the time of the first study vaccination through approximately Day 64.

MAAEs, SAEs, and AESIs (PIMMCs) will be documented and reported from the time of the first study vaccination through approximately 12 months after the second study vaccination (the entire time the participant is followed from first vaccination until study completion), i.e., through approximately Day 380.

#### 9.3.1 Serious Adverse Events

Any AE that meets a protocol-defined serious criterion must be submitted immediately (within 24 hours of site awareness) on an SAE form to the DMID Pharmacovigilance Group, at the following address:

DMID Pharmacovigilance Group Clinical Research Operations and Management Support (CROMS) [name] [name] [name]

SAE Hot Line: [name] (US) or [name] (outside US) SAE [contact] (US) or [name] (outside US)

SAE Email Address: [contact]

In addition to the SAE form, selected SAE data fields must also be entered into Advantage eClinicalSM. Please see the protocol-specific MOP for details regarding this procedure.

Other supporting documentation of the event may be requested by the DMID Pharmacovigilance Group and should be provided as soon as possible.

The DMID Medical Monitor and DMID Clinical Project Manager will be notified of the SAE by the DMID Pharmacovigilance Group.

The DMID Medical Monitor will review and assess the SAE for regulatory reporting and potential impact on participant safety and protocol conduct.

At any time after completion of this trial, if the site PI or appropriate sub-investigator becomes aware of an SAE that is suspected to be related to study product, the site PI or appropriate sub-investigator will report the event to the DMID Pharmacovigilance Group.

## 9.3.2 Regulatory Reporting for Studies Conducted Under DMID-Sponsored IND

Following notification from the site PI or appropriate sub-investigator, DMID, the Investigational New Drug (IND) sponsor, will report any suspected adverse reaction that is both serious and unexpected. DMID will report an AE as a suspected adverse reaction only if there is evidence to suggest a causal relationship between the drug and the AE. DMID will notify the FDA and all investigators (i.e., the participating VTEU site PI to whom the sponsor is providing drug under its IND(s) or under any PI's IND(s)) in an IND safety report of potential serious risks from clinical trials or any other source, as soon as possible, but in no case later than 15 calendar days after the sponsor determines that the information qualifies for reporting as specified in 21

CFR Part 312.32. DMID will also notify the FDA of any unexpected fatal or life-threatening suspected adverse reaction as soon as possible, but in no case later than 7 calendar days after the sponsor's initial receipt of the information. Relevant follow up information to an IND safety report will be submitted as soon as the information is available. Upon request from the FDA, DMID will submit to the FDA any additional data or information that the agency deems necessary, as soon as possible, but in no case later than 15 calendar days after receiving the request.

All serious adverse events designated as "not related" to study product(s) will be reported to the FDA at least annually in a summary format.

## 9.3.3 Reporting of Pregnancy

Upon awareness, pregnancies occurring in participants will be recorded on the Pregnancy Report eCRF. All pregnancies reported during the course of this trial will be followed to pregnancy outcome, if allowable to the participant. With the participant's permission, we will continue to follow the participant for safety and immune response. If the participant becomes pregnant after the first vaccination, the second vaccination will not be given.

## 9.4 Type and Duration of Follow-up of Participants after Adverse Events

Non-serious unsolicited AEs will be collected, assessed, and followed through resolution from the time of first study vaccination through approximately Day 64.

MAAEs, SAEs, and AESIs (PIMMCs) will be collected, assessed and followed from the time of the first study vaccination through resolution even if this extends beyond the trial-reporting period (approximately 12 months after the second study vaccination, i.e., approximately Day 380).

Resolution of an AE/SAE is defined as the return to pretreatment status or stabilization of the condition with the expectation that it will remain chronic.

Follow-up procedures, evaluations, and outcomes will be recorded on the appropriate eCRF.

## 9.5 Halting Rules

## 9.5.1 Individual Halting Rules

- Any participant experiences ulceration, abscess, or necrosis at the injection site from vaccination until 7 days later (Days 1 through 8, inclusively, for the first vaccination and Days 15 through 22, inclusively, for the second vaccination. Should the second vaccination occur after Day 15, the reactogenicity period will occur from the day of vaccination until 7 days later)
- Any participant experiences laryngospasm, bronchospasm, or anaphylaxis within 24 hours after administration of the study products
- Any participant experiences generalized urticaria (defined as urticarial lesions occurring at more than two body parts) within 72 hours after administration of study product.
- Any participant experiences an SAE (except for accident or trauma) after administration of the study product.
- Any participant experiences a grade 3 AE including lab, local, or systemic solicited reactogenicity events (excluding measured grades of ecchymosis, erythema, and edema/induration alone)

## 9.5.2 Study Halting Rules

Additional enrollment and study interventions/administration of study products in this trial will be halted for SMC review/recommendation if any of the following are reported after the first study vaccination:

- Any participant experiences ulceration, abscess or necrosis at the injection site in the week after vaccination (Days 1 through 8, inclusively, for the first vaccination and Days 15 through 22, inclusively, for the second vaccination; should the second vaccination occur after Day 15, the reactogenicity period will occur from the day of vaccination until 7 days later) that is considered related to study product administration.
- Any participant experiences laryngospasm, bronchospasm or anaphylaxis within 24 hours after administration of study product that is considered related to study product.

- Two or more participants experience generalized urticaria (defined as urticarial lesions occurring at more than two body parts) within 72 hours after administration of study product that is considered related to study product.
- Any participant experiences an SAE after administration of study product that is considered related to study product.
- Any participant develops a PIMMC after administration of study product from receipt of study product until last study visit (approximately Day 380).
- Three or more participants experience a grade 3 injection site or systemic solicited adverse event (excluding measured grades of ecchymosis, erythema, and edema/induration alone).
- Three or more participants experience the same grade 3 AE (unsolicited and laboratory abnormality), in the same HLGT by MedDRA coding, considered related to study product.

Grading scales for solicited injection site and systemic (subjective and quantitative) reactions are included in Section 9.2.2. Grading scales for clinical safety laboratory AEs are included in Section 9.2.3.

If any of the halting rules are met following any participant receipt of study vaccination, then this trial will not continue with the remaining enrollments or study vaccinations without a review by and recommendation from the SMC to proceed.

DMID retains the authority to suspend additional enrollment, study interventions, and administration of study products during this trial, as applicable.

The DMID Medical Monitor is empowered to stop enrollment and study vaccinations if AEs that meet the halting criteria are reported.

## 9.6 Safety Oversight

#### 9.6.1 Independent Safety Monitor (ISM)

For this clinical trial, an ISM is not required. The site PI or appropriate sub-investigator will send to the DMID Medical Monitor a summary of the events and include the site PI assessments.

#### 9.6.2 Safety Monitoring Committee

Safety oversight will be conducted by an SMC that is an independent group of experts that monitors participant safety and advises DMID. The SMC members will be separate and independent of study personnel participating in this trial and will not have scientific, financial, or other COI related to this trial. The SMC will consist of members with appropriate expertise to contribute to the interpretation of the data from this trial.

The SMC will operate under the rules of a DMID-approved charter that will be written at the organizational meeting of the SMC. At this time, each data element that the SMC needs to assess will be clearly defined. Procedures for SMC reviews/meetings will be defined in the charter. The SMC will review applicable data to include, but not limited to, study progress and clinical, safety, reactogenicity, and immunogenicity data. Reports may include enrollment and demographic information, medical history, concomitant medications, physical assessments, clinical laboratory values, dosing compliance, solicited and unsolicited AEs, MAAEs, SAEs, and AESIs (PIMMCs). The SMC will review SAEs on a regular basis and ad hoc during this trial. The DMID Medical Monitor will be responsible for reviewing SAEs in real time.

The SMC will conduct the following reviews:

- An Organizational Meeting that occurs prior to participant enrollment
- Ad hoc when a halting rule is met, or DMID/SMC chair may convene an ad hoc meeting if there are immediate concerns regarding observations during the course of this trial. The DMID Medical Monitor is empowered to stop enrollment and study vaccinations if AEs that meet the halting criteria are reported.
- Final review meeting: 6 to 8 months after database lock to review the cumulative unblinded safety and immunogenicity data for this trial. The data will be provided in a standard summary format. The SMC may be asked to provide recommendations in response to questions posed by DMID.

Additional data may be requested by the SMC, and interim statistical reports may be generated as deemed necessary and appropriate by DMID. The SMC may receive data in aggregate and presented by treatment arm. The SMC may also be provided with expected and observed rates of the expected AEs in an unblinded fashion and may request the treatment assignment be unblinded for an individual participant if required for safety assessment. The SMC will review grouped and unblinded data in the closed session only. As an outcome of each review/meeting, the SMC will make a recommendation as to the advisability of proceeding with study vaccinations, as applicable, and to continue, modify or terminate this trial.

## 10 CLINICAL MONITORING

## 10.1 Site Monitoring Plan

Site monitoring is conducted to ensure that the human participants' protections, study and laboratory procedures, study interventions/administration of study products, and data collection processes are of high quality and meet sponsor and ICH E6 GCP guidelines and applicable federal regulations, and that this trial is conducted in accordance with the protocol, protocol-specific MOP and applicable sponsor SOPs. DMID, the sponsoring agency, or its designee will conduct site-monitoring visits as detailed in the clinical monitoring plan. DMID-designated clinical monitors will verify that this trial is conducted, and data are generated, documented (recorded), and reported in compliance with the protocol, ICH E6 GCP guidelines, and applicable regulatory requirements. Clinical monitoring reports will be submitted to DMID.

Site visits will be made at standard intervals as defined by DMID and may be made more frequently as directed by DMID. Monitoring visits will include, but are not limited to, review of regulatory files, accountability records, eCRFs, ICFs, medical and laboratory reports, and protocol and GCP compliance. Site monitors will have access to each participating VTEU site, study personnel, and all study documentation according to the DMID-approved site monitoring plan. Study monitors will meet with site PIs to discuss any problems and actions to be taken and document visit findings and discussions.

## 11 STATISTICAL CONSIDERATIONS

#### 11.1 Introduction

The goal of this clinical study is to assess in healthy adults, 18-45 years of age, the safety, reactogenicity, and immunogenicity of two doses of AV7909 administered as either the thermostable lyophilized product or as the liquid product.

#### 11.2 Study Hypotheses

This Phase I study is not designed to test a formal null hypothesis. Rather, it is intended to obtain sufficient data to obtain meaningful estimates of the immune response induced by either vaccine formulation, and to uncover any safety issues that occur at a sufficiently high rate that they might be observed in a study of this size. The sample size facilitates formal testing of selected hypotheses as discussed in Section 11.4.3, along with the probability of observing safety outcomes and the precision of immunogenicity outcomes.

#### 11.3 Study Outcome Measures

Please refer to Study Outcome Measures outlined in Table 1.

#### 11.4 Sample Size Considerations

Please refer to Study Design outlined in Section 4.

#### 11.4.1 Study Population

The study population for this clinical trial includes males and non-pregnant females, 18-45 years of age, who are in good health and meet all eligibility criteria. The participants will be recruited from the general population at one participating VTEU site.

#### 11.4.2 Participant Enrollment and Follow-up

Based on the accrual rates observed in similar studies, it seems reasonable to expect that the participating VTEU will be able to enroll this trial in a timely fashion, about 12 weeks from first participant vaccinated until the final participant receives his/her first vaccination.

A total of 40 participants will be enrolled. Assuming up to 10% drop out by Day 64, it is expected that at least 18 subjects per group will be available for the primary immunogenicity analysis.

## 11.4.3 Sample Size

While this study is not designed to test any specific null hypothesis, the following illustrates the precision and power that are available for select estimates and comparisons of interest, based on the planned sample size of N=20 participants per study arm.

Table 11 indicates the probability of observing one or more safety events, such as solicited injection site or systemic reactogenicity events or an unsolicited AE of a particular type, for a single treatment arm (N=20), and for all enrolled subjects (N=40).

**Table 11: Probability (%) to Detect Safety Events Emmes** 

Event	N = 20	N = 40
Frequency		
≥10%	87	98
Very Common		
≥1%	18	33
Common		
≥0.1%	1	3
Uncommon		
≥0.01%	< 0.1	< 0.1
Rare		

Binomial confidence intervals (CI) are widest (have the least precision) when the response rate is 50%. Table 12 is presented to indicate the worst-case scenario for precision of observed exact (Clopper-Pearson) binomial confidence intervals.

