**Table 12: Precision of Binomial Confidence Intervals** 

N	95% CI			
20	27-73			
40	34-66			

For each of the primary immunogenicity objectives, a power analysis is provided below for testing the following hypotheses with the planned sample size, where  $p_c$  = probability of response in comparator arm; where  $p_e$  = probability of response in experimental arm.

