# 5. SAMPLE SIZE CONSIDERATIONS

This study is planned to enroll a total of 40 subjects, with 20 subjects in each study arm. This phase I study is not designed to test a formal null hypothesis. Rather, it is intended to obtain sufficient data to obtain meaningful estimates of the immune response induced by either vaccine formulation and to uncover any safety issues that occur at a sufficiently high rate that they might be observed in a study of this size. As such, the type one error rate, alpha = 0.05, is not adjusted for multiple comparisons. While this study is not designed to test any specific null hypothesis, the following tables illustrate the precision and power that is available for select estimates and comparisons of interest.

Table 2 indicates the probability of observing one or more safety events, such as solicited injection site or systemic reactogenicity events or an unsolicited AE of a particular type, for a single treatment arm (N=20), and for all enrolled subjects (N=40).

Binomial confidence intervals (CI) are widest (have the least precision) when the response rate is 50%. Table 3 is presented to indicate the worst-case scenario for precision of observed exact (Clopper-Pearson) binomial confidence intervals.

For each of the primary immunogenicity objectives, a power analysis is provided below for testing the following hypotheses with the planned sample size, where  $p_c =$  probability of response in comparator arm; where  $p_c =$  probability of response in experimental arm.

Test for difference in proportion responders:

 $H_0: p_c - p_e = 0$ ; No difference in response probabilities

H1:  $p_c - p_e \neq 0$ ; difference in response probabilities

Table 4 illustrates the minimum detectable differences in the probability of responding (e.g., attaining seroconversion or  $NF_{50} \ge 0.56$  [seroprotection]) between participants who receive AV7909 as the lyophilized formulation or liquid formulation using a two-sided likelihood ratio test with 80% power and alpha = 0.05. It is assumed that up to 10% of subjects (N=2) will be excluded from the per-protocol analysis in each group. Seroconversion rates of 10% to 60% are considered.

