### 9.7.1 Sample Size

### Table 2:Power (%) to Detect Safety Events

Event Frequency	Single Treatment Arm N=20	All Enrolled Subjects N=40
10% Very Common	87	98
1% Common	18	33
0.1% Uncommon	1	3
0.01% Rare	<0.1	<0.1

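### Both rare-event cells in the safety detection table are wrong: at a 0.01% event rate the chance of seeing at least one event is 0.20% (N=20) and 0.40% (N=40), not below 0.1%

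*Protocol*

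**What the plan says.** Protocol section 11.4.3 introduces Table 11 by saying that it "indicates the probability of observing one or more safety events", for one arm of 20 and for all 40 enrolled. The table is titled "Table 11: Probability (%) to Detect Safety Events Emmes", so its cells are percentages. Its rows are event frequencies of at least 10%, 1%, 0.1% and 0.01%. In the last row, labelled rare, both cells read < 0.1.

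The SAP carries the same table. Section 5 states that "Table 2 indicates the probability of observing one or more safety events", and the table itself is captioned "Power (%) to Detect Safety Events". Its rows show 10%, 1%, 0.1% and 0.01% without the at-least sign, and both rare cells again read < 0.1.

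**The concern.** A rate of 0.01% is 1 in 10,000. With 20 participants the expected number of events is 20 × 0.0001 = 0.002, and with 40 it is 0.004. When events are this rare, the chance of at least one is almost equal to the expected number, so the cells should be close to 0.2% and 0.4%. A printed bound below 0.1% is too low for both.

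The Protocol's at-least sign makes the conflict sharper. The chance of seeing an event rises with the event rate, so the values at exactly 0.01% are the smallest the row allows, and no rate in the row satisfies the printed bound.

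The table is part of the sample-size justification. Protocol section 11.2 gives uncovering sufficiently frequent safety issues as an aim and refers to section 11.4.3 for the probability of observing them. What is at stake is the accuracy of a stated detection probability in two documents, not a design decision.

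**Working it through.** **Inputs.** N = 20 and N = 40, the at-least-one-event definition and the percent unit come from Protocol section 11.4.3 and Table 11. The SAP agrees (section 5 and Table 2). Event rates p are 0.10, 0.01, 0.001 and 0.0001.

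**Formula.** P(at least one event) = 1 − (1 − p)^N.

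| Event rate | N=20 computed | N=20 printed | N=40 computed | N=40 printed |
|---|---|---|---|---|
| 10% | 87.84% | 87 | 98.52% | 98 |
| 1% | 18.21% | 18 | 33.10% | 33 |
| 0.1% | 1.98% | 1 | 3.92% | 3 |
| 0.01% | 0.1998% | < 0.1 | 0.3992% | < 0.1 |

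The first three rows reproduce the printed figures once the decimals are dropped. This confirms that the formula is the one intended and isolates the failure to the last row:

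- N=20: 1 − 0.9999^20 = 0.0019981, or 0.20%.
- N=40: 1 − 0.9999^40 = 0.0039922, or 0.40%.

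**Could another reading give < 0.1?**

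- *Rounding or truncation.* To one decimal, rounding gives 0.2 and 0.4, and truncation gives 0.1 and 0.3. Whole percents would give 0, for which a true bound is < 1.
- *Drop-out.* Protocol section 11.4.2 allows for attrition ("Assuming up to 10% drop out by Day 64"). With 18 per arm and 36 in total the values are 0.18% and 0.36%.
- *Poisson approximation.* 1 − exp(−Np) gives 0.1998% and 0.3992%.
- *Each of the two doses counted as an exposure.* With 40 and 80 exposures the values are 0.40% and 0.80%, further from the bound.
- *Proportions instead of percentages.* 0.0020 and 0.0040 are indeed below 0.1, but both titles say percent and every other cell is a percentage.

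**What would make the bound true?** At a rate of 0.01%, ln(0.999)/ln(0.9999) = 10.0, so N could be no more than 10. At the tabulated sizes the rate would have to be below 1 − 0.999^(1/20) = 0.0050% for N=20, or 1 − 0.999^(1/40) = 0.0025% for N=40. Both are lower than the tabulated 0.01%.

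**Display of the other cells.** The entries 87, 98, 1 and 3 are truncated; rounding would give 88, 99, 2 and 4. The next table, "Table 12: Precision of Binomial Confidence Intervals", is rounded: exact Clopper-Pearson limits for 10/20 are 27.20–72.80% (printed 27-73) and for 20/40 are 33.80–66.20% (printed 34-66). This is a difference of convention, not an error, though in relative terms it matters in the 0.1% row, where 1.98 is shown as 1.

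**The case against.** The strongest counter-argument is about weight. Both documents say that the study is not built to test a specific hypothesis and that these tables are illustrative. The safety aim is limited to problems frequent enough to appear in a study this small, and a 1-in-10,000 event lies outside it whether the chance of seeing one is 0.1%, 0.2% or 0.4%. That is correct, and it is why the point is minor. It does not make the printed bound true.

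A second argument concerns display. SAP section 13 reports percentages to the nearest whole number and shows non-zero values under 1% as < 1, so < 1 in both cells would be a correct minimal repair, and one decimal throughout is a preference. That section is written for reported results, not for a planning table, and it does not support < 0.1 in any case. The preference for one decimal is conceded to be optional.

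Third, the attrition assumption concerns the immunogenicity analysis, whereas the safety population is everyone given the first dose. This is also correct. The figures at 18 and 36 are included only to rule out an explanation a reader might try.

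A fault in reading the PDF is unlikely, since the same entry appears separately in both documents.

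**Conclusion.** The concern holds. Two of the eight cells are wrong, in both the Protocol and the SAP. The correct values exceed the printed upper bound by factors of about 2.0 (N=20) and 4.0 (N=40). In absolute terms the gaps are small: 0.20 − 0.10 = 0.10 and 0.40 − 0.10 = 0.30 percentage points, measured from the bound. The error understates the chance of detection. The calculation assumes only independent participants with a common event rate, which is also the basis on which the remaining cells reproduce. Severity is minor.

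**What to change.** In Protocol Table 11 and SAP Table 2, replace the 0.01% row with 0.2 (N=20) and 0.4 (N=40). For consistency, show all cells to one decimal: 87.8 and 98.5; 18.2 and 33.1; 2.0 and 3.9; 0.2 and 0.4. Optionally, retitle SAP Table 2 as the probability (%) of at least one event, since SAP section 5 describes that quantity and no test is involved. The cost is one table edit in each of two documents, with no change to design, sample size or analysis.
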